# 9.4.2 Safety Endpoints

Safety and tolerability will be assessed by clinical review of all relevant parameters including adverse events, laboratory values and vital signs. The a priori safety events of interest are as follows: complex sleep-related behaviors, sleep paralysis (including sleep onset paralysis [adjudicated]), hypnagogic or hypnopompic hallucinations, somnolence resulting in discontinued intervention, falls (adjudicated to rule out cataplexy), suicidal ideation and/or behaviors, selected events associated with potential for abuse, cataplexy (adjudicated). Those events which consist of multiple AE terms (e.g., complex sleep-related behaviors, selected events associated with potential for abuse) will be defined separately prior to unblinding.

#### 9.5 Analysis Populations

#### 9.5.1 Efficacy Analysis population

The FAS population will serve as the primary population for the analysis of efficacy data in this study. The FAS population consists of all randomized participants who have at least one assessment of delirium by DSM-5 following administration of at least one dose of study medication. Occurrences of delirium after randomization but prior to the first dose of study medication will thus be excluded from the analysis.

A supportive analysis using the Per-Protocol (PP) population may be performed for the primary efficacy endpoint if there is a substantial number of protocol violators (>10% of FAS) that will be excluded from the PP population. The PP population excludes participants due to major deviations from the protocol that may substantially affect the results of the primary efficacy endpoint. Potential deviations that may result in the exclusion of a participant from the PP population include:

- Significant violation to the inclusion/exclusion criteria that may affect the results of the primary efficacy endpoint
- Missing assessment of delirium by DSM-5 at any time during the assessment period
- Treatment duration of less than 5 days, with the exception of discontinuation due to delirium as assessed by DSM-5
- Missed dose(s) of study treatment at any time during the trial
- Use of prohibited concomitant medications

The final determination on major protocol deviations, and thereby the composition of the PP population, will be made prior to the unblinding of the database and will be documented in a separate memo.

Participants will be included in the treatment group to which they are randomized for the analysis of efficacy data.

# 9.5.2 Safety Analysis Population

Safety analyses will be conducted in the APaT population, which consists of all randomized participants who received at least one dose of study treatment. Participants will be included in the treatment group corresponding to the study treatment they actually received for the analysis of safety data using the APaT population. For most participants this will be the treatment group to which they are randomized. Participants who take incorrect study treatment for the entire treatment period will be included in the treatment group corresponding to the study received.

At least one laboratory or vital sign measurement obtained subsequent to at least one dose of study treatment is required for inclusion in the analysis of the respective safety parameters. To assess change from baseline, a baseline measurement is also required.

#### 9.6 Statistical Methods

Unless otherwise stated, all statistical tests will be conducted at the  $\alpha$ =0.05 (2-sided) level.

#### 9.6.1 Statistical Methods for Efficacy Analyses

This section describes the statistical methods that address the primary and secondary objectives. Methods for supportive analyses and those related to exploratory objectives will be described in the sSAP.

#### Primary endpoint

The treatment difference in the proportion of participants with delirium during the assessment period as assessed by DSM-5, along with the corresponding 95% CI and the p-value based on the Miettinen and Nurminen method, will be provided. The analysis will be stratified by hospitalization reason (acute disease, elective surgery) and age category (<75 years,  $\geq$ 75 years). The Cochran-Mantel-Haenszel weight will be used to obtain stratum-adjusted proportion difference.

Missing assessments will be considered not having delirium. A supportive analysis using survival analytic methods will be conducted to assess the robustness of the conclusion from the primary analysis to the assumption about the missing assessment of delirium. Details will be described in the sSAP.

#### Secondary endpoints

The proportion of participants with delirium during the assessment period as assessed by DRS-R-98 will be analyzed in the same manner as the primary endpoint. The severity of delirium during the assessment period as assessed by DRS-R-98 will be compared between treatments using an aligned rank test [Mehrotra DV, et al. 2010], taking into consideration the potential non-normality of the data. Within each stratum, the data from individual

participants will be pooled across treatments and transformed by subtracting the Hodges-Lehmann estimate. The transformed values from all strata will then be analyzed for treatment comparison using the unstratified Wilcoxon rank-sum test.

Missing responses for the individual items of DRS-R-98 will be scored as the midpoint of the smallest and the largest possible scores (e.g., as 1.5 for those items rated as 0, 1, 2 or 3), which is consistent with the approach employed in the validation of DRS-R-98 [Trzepacz PT, et al. 2001]. If the assessment is entirely missing on a particular day, the score will be considered missing on that day.

Table 5 summarizes key efficacy analyses.

Endpoint/Variable (Description, Time Point)	Statistical Method	Analysis Population	Missing Data Approach			
Primary Hypothesis						
Proportion of participants with delirium during the assessment period as assessed by DSM-5	Stratified Miettinen and Nurminen †	FAS	Missing data due to missed assessments will be considered not having delirium			
Secondary Objective #1						
Severity of delirium during the assessment period as assessed by DRS-R-98	Aligned rank test	FAS	Missing responses for the individual items of DRS-R-98 will be scored as the midpoint of the smallest and the largest possible scores. If the assessment is entirely missing on a particular day, the score will be considered missing on that day.			
Secondary Objective #2						
Proportion of participants with delirium during the assessment period as assessed by DRS-R-98, defined as the proportion of participants with the maximum total score of 14.5 or greater during the assessment period	Stratified Miettinen and Nurminen †	FAS	Missing responses for the individual items of DRS-R-98 will be scored as the midpoint of the smallest and the largest possible scores. If the assessment is entirely missing on a particular day, the score will be considered missing on that day.			

Table 5 Analysis Strategy for Key Efficacy variables	Table 5	Analysis Strategy for Key Efficacy Varial	oles
--	---------	---	------

† Miettinen and Nurminen method stratified by hospitalization reason (acute disease, elective surgery) and age category (<75 years,  $\geq$ 75 years). The Cochran-Mantel-Haenszel weight will be used to obtain stratum-adjusted proportion difference.

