## **Medical Conditions**

- 1. Has moderate or severe dementia.
- 2. Has whose APACHE II is 31 or more at Screening (Only for acute disease).
- 3. Has a history of epilepsy or Parkinson's disease.
- 4. Currently uses any of psychotropic agents, or has unstable mental condition including schizophrenia, other mental diseases, bipolar disorder and major depression.
- 5. Has a history of drug or alcohol abuse within 5 years before Screening, or consumes over 60 g per day of alcohol on average (e.g., 60 g alcohol is 3 *goes* of Japanese sake, 3 middle bottles of beer, or 5 glasses of wine), or has alcoholic disease such as alcoholic liver disease or gastritis alcoholic.
- 6. Has delirium as assessed by DSM-5 or DRS-R-98 (total score ≥14.5) during the screening period.
- 7. Is at imminent risk of self-harm or of harm to others in the opinion of the investigator. Participants must be excluded if they report suicidal ideation with intent, with or without a plan or method in the *past 2 months* or suicidal behavior in the *past 6 months*.
- 8. Has history of narcolepsy or cataplexy.
- 9. Has history of hypersensitivity to suvorexant.
- 10. Meets any contraindication or warning listed on package inserts of suvorexant and which are not contained in the exclusion criteria of this protocol.

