#### 6.3.2 Stratification

Intervention randomization will be stratified according to the following factors:

1. Hospitalization reason (acute disease, elective surgery)

If either the proportion of participants hospitalized due to acute disease or those hospitalized due to elective surgery exceeds approximately 60% of the total targeted sample size, the remaining participants will only be enrolled into the other stratum within this stratification factor.

2. Age category (<75 years,  $\geq 75$  years)

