## 8.9.1.2 Baseline/Visit 2 (until Randomization)

The qualified rater will assess DSM-5 and DRS-R-98 on the day of randomization. The participant will complete RCSQ.

After reviewing whether the participant meets the inclusion and does not meet exclusion criteria based on the above assessments, the eligible participant will be registered and randomized. In addition, the participant will receive appropriate non-pharmacotherapy based on his/her condition (See Section 5.3.1).

The received randomization number will be entered in the participant identification card. The study medication will be prescribed to the participant according to the Component ID. The investigator will instruct the participant to take one tablet of study medication once daily orally before bedtime from the day.

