#### 9.4 Analysis Endpoints

Key efficacy and safety endpoints are listed below. The baseline value is defined as the last available measurement prior to the first dose of study medication.

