#### 9.4.1 Efficacy Endpoints

The primary efficacy endpoint is the proportion of participants with delirium during the assessment period as assessed by DSM-5.

The secondary efficacy endpoints are:

1. Severity of delirium during the assessment period as assessed by DRS-R-98, defined as the maximum (i.e., worst) of total score among those obtained daily during the assessment period.

2. Proportion of participants with delirium during the assessment period assessed by DRS-R-98, defined as the proportion of participants with the maximum total score of 14.5 or greater during the assessment period.

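### The test of maximum DRS-R-98 (Secondary Objective #1) ignores the pre-randomisation DRS-R-98 total; it is valid, but loses power if baseline predicts the maximum within strata

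*Combined protocol and SAP*

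**What the plan says.** Section 9.4.1 gives the endpoint as severity on DRS-R-98, "defined as the maximum (i.e., worst) of total score among those obtained daily during the assessment period". Under Secondary endpoints in Section 9.6.1, severity "will be compared between treatments using an aligned rank test". Each stratum is centred by a Hodges-Lehmann estimate taken over both arms together, and then: "The transformed values from all strata will then be analyzed for treatment comparison using the unstratified Wilcoxon rank-sum test". Table 5 repeats the method. Neither place has a baseline term.

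A baseline total exists. Section 8.9.1.2 states: "The qualified rater will assess DSM-5 and DRS-R-98 on the day of randomization". The Schedule of Activities puts this rating before randomisation. Exclusion criterion 6 depends on its total: "Has delirium as assessed by DSM-5 or DRS-R-98 (total score ≥14.5) during the screening period". Section 9.4 adds: "The baseline value is defined as the last available measurement prior to the first dose of study medication". Section 9.6.1 makes no use of that definition for efficacy.

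The sSAP was not available. Its scope is limited by the opening of Section 9.6.1: "Methods for supportive analyses and those related to exploratory objectives will be described in the sSAP". The main method for this objective is therefore the one in 9.6.1.

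**The concern.** The outcome is the same scale as the baseline, rated again over the following days. The scale has orientation, attention, memory and visuospatial items (Section 3), and people with mild dementia or mild cognitive impairment can enter (Section 5.1). Part of each participant's maximum may therefore be a stable personal level that was already visible before randomisation. If so, the planned test treats predictable variation as noise. The trial would then have a lower chance of detecting a real effect on severity than its own data allow.

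Nothing else is at stake. The planned test does not inflate the type I error. Section 9.6.1 names a test but no effect estimator for this endpoint, so no claim is made about the precision of an estimate.

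**Working it through.** **1. The plan's own figure.** No power, SD or correlation is given for this endpoint. The only efficacy power is for the primary endpoint (Section 9.9.1: 100 per arm, two-sided 0.05). With a pooled null variance, power = Φ{[(p0 − p1) − 1.96·√(2p̄(1 − p̄)/n)] / √([p0(1 − p0) + p1(1 − p1)]/n)}.
- 30% vs 11.6%: p̄ = 0.208, so (0.184 − 1.96 × 0.0574)/0.0559 = 1.28 and power is 89.95% (stated 90%).
- 30% vs 13.7%: power is 80.1% (stated 80%).

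The primary figures reproduce. The delirium rates are borrowed below.

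**2. Analytic guide.** Removing a covariate with within-stratum correlation r multiplies the outcome variance by 1 − r². If unadjusted power is 80%, adjusted power is Φ(2.80/√(1 − r²) − 1.96), and the equivalent unadjusted total N is 200/(1 − r²).

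| r | adjusted power | equivalent N |
|---|---|---|
| 0 | 80.0% | 200 |
| 0.2 | 81.6% | 208 |
| 0.3 | 83.6% | 220 |
| 0.4 | 86.4% | 238 |
| 0.5 | 89.9% | 267 |

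**3. Simulation, structure 1.** All scores are assumed.
- 200 participants in 4 strata of 50, with 25 per arm in each.
- Baseline = stratum mean (6, 6.5, 7, 7.5) + stable trait + noise, total SD 4, rounded, floor 0, totals of 14.5 or more excluded.
- 5, 6 or 7 daily scores (equally likely) = same trait + new noise.
- Delirium in 30% vs 13.7%, onset day uniform on 1 to 5, adding a jump of mean 12 and SD 4 (minimum 3). No scores follow onset, as Sections 4.1 and 7.1 require.
- The outcome is the maximum. The trait SD is varied to move r. 5,000 trials per setting.

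The adjusted test is the rank analysis of covariance set out under the fix. Differences were taken before rounding.

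| r | planned | adjusted | change (points) |
|---|---|---|---|
| 0.00 | 35.1% | 35.0% | −0.1 |
| 0.13 | 35.5% | 35.4% | −0.1 |
| 0.24 | 37.0% | 38.6% | +1.6 |
| 0.30 | 36.9% | 38.7% | +1.7 |
| 0.40 | 39.2% | 44.3% | +5.2 |
| 0.54 | 41.5% | 53.5% | +12.0 |

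Monte Carlo 95% margins on the changes are 0.4 to 1.3 points.

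**4. Structure 2, less favourable.** Half the participants have no stable trait (entry by delirium history only). Strata are 42, 78, 28 and 52, noise SD is 2.5, and there are 3,000 trials per setting. Changes: +0.1 at r = 0.00, +1.1 at 0.17, +3.2 at 0.28, +4.2 at 0.36.

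**5. A third structure.** Baseline is skewed and capped at 14, the maximum is generated directly, delirium is 30% vs 11.6%, and there are 3,000 trials per setting. Planned vs adjusted power: 61.3% vs 61.1% at r = 0, 59.4% vs 61.7% at 0.22, 57.3% vs 63.9% at 0.38, 53.5% vs 66.8% at 0.51.

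**6. Type I error.** With equal delirium rates, structure 1 rejected in 4.7% to 5.4% (planned) and 4.4% to 5.8% (adjusted) at 4,000 trials per setting. Checks with 20,000 trials gave 5.3%/5.5% at r = 0.48 and 5.0%/5.1% at r = 0.53. Structure 2 gave 5.0% to 5.3% (planned) and 4.8% to 5.3% (adjusted). Both tests hold their level.

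**The case against.** The best reply is that this is a preference between two valid tests, on an endpoint with no hypothesis, no stated power and no alpha control, and that the benefit depends on a correlation the documents never give. Several features could keep r low: the 14.5 entry cap, the exclusion of moderate and severe dementia, entry on a history of delirium alone, and an outcome that is a worst-day maximum. For elective surgery the baseline also precedes the operation, whereas Section 4.3.2 puts typical onset about 3 days after it; none of the simulations models that. In one rebuild of structure 1, reaching r = 0.39 took a stable trait accounting for about 49% of score variance. The sSAP may also already contain a supportive adjusted analysis.

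All of this stands as a limit on size. It does not remove the point. When r is near 0 the adjustment loses almost nothing, so not knowing r is no argument for leaving baseline out. An sSAP supportive analysis would leave the main test unchanged.

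The unnamed strata are only a missing detail. Section 9.6.1 does not list them for this test, and the Table 5 footnote that does belongs to the Miettinen-Nurminen rows. The randomisation factors in Section 6.3.2 are the obvious reading, and nothing here depends on this.

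**Conclusion.** The point holds as an improvement in efficiency; it is not an error in the plan. The test for Secondary Objective #1 leaves out a baseline total that is already scheduled for every participant. On assumed scores, adjusting gains a negligible amount up to r of about 0.2, 2 to 3 points near 0.3, about 5 near 0.4 and about 12 near 0.55. The third structure gave somewhat larger gains at similar r.

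The direction rests only on baseline predicting the maximum within strata. The sizes rest on the assumed score distributions. The absolute powers (35% to 41% planned in structure 1, 42% to 47% in structure 2) should not be relied on. Confidence in the practical gain is moderate, because r is unknown.

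**What to change.** Before database lock, specify for Secondary Objective #1 in Section 9.6.1 and Table 5:

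1. Name the strata, presumably hospitalisation reason by age category.
2. Within each stratum, subtract the Hodges-Lehmann estimate pooled over arms from the maximum DRS-R-98 total. Do the same, with its own estimate, for the baseline total.
3. Rank each set of aligned values over all participants and regress outcome rank on baseline rank, ignoring treatment.
4. Divide the difference between arms in mean residual by √(s²(1/n1 + 1/n0)), where s² is the residual variance over both arms together. Refer the result to the standard normal, two-sided at 0.05.
5. Score missing baseline items by the midpoint rule already planned. Give a participant with no baseline total an aligned baseline of 0, so that nobody leaves the FAS. In a check with 10% of baselines missing, this rule rejected in 5.3% under the null, and power was 37.7% planned against 42.3% adjusted.
6. Keep the present unadjusted aligned rank test as the sensitivity analysis.

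The cost is a few lines of text and code, with no new data. Section 9 lets changes to nonconfirmatory analyses be recorded in the sSAP before lock, and this objective lies outside the single primary hypothesis. The statistical downside is a power change of under 1 point if r is near 0: −0.1 and +0.1 points in structures 1 and 2, −0.2 in the third, and −0.2 to −0.5 in smaller repeat runs.

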#### 4 STUDY DESIGN

## 4.1 Overall Design

This is a randomized, placebo-controlled, parallel-group, multi-site, double-blind clinical study to evaluate the efficacy and safety of suvorexant for reducing incidence of delirium in Japanese participants at high risk of delirium.

This study consists of a screening period of up to 14 days (for acute disease, within 24 hours after admission; for elective surgery, within 14 days before admission), an assessment period of up to 8 days (from the first dose of study medication to the last assessment visit: for 6 to 8 days), and a follow-up period of 14 days.

The target population includes Japanese participants at high risk of delirium between the ages of 65 and 90 years, inclusive. Participants judged as eligible in the screening period will be randomized in a 1:1 ratio to receive either suvorexant or placebo at Visit 2, and they will take one tablet of study medication (suvorexant 15 mg tablet or matching placebo tablet) once daily (q.d.) orally before bedtime for 5-7 days in a double-blind manner. The participants who develop delirium after randomization but prior to the first dose of study medication will be withdrawn from the study without the study medication administration. The participants hospitalized due to elective surgery will receive surgery on the next day or 2 days after admission/the first dose of study medication and will take study medications for 4 days at least after surgery. For the participants who develop delirium during the assessment period, the study intervention is discontinued at this timing. The use of prohibited medications including antipsychotics for treatment of delirium is allowed in the opinion of the investigator after completion or following a decision of discontinuation of study medication administration. The follow-up visit 14 days after last dose of study intervention will be performed for all participants received study medication.

The target number of participants receiving study medication is approximately 200 participants. Intervention randomization will be stratified according to hospitalization reason (acute disease, elective surgery) and age category (<75 years,  $\geq$ 75 years). If either the proportion of participants hospitalized due to acute disease or those hospitalized due to elective surgery exceeds approximately 60% of the total targeted sample size, the remaining participants will only be enrolled into the other stratum within this stratification factor.

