#### AND

- b) Meets any one of followings at Screening;
  - Has severe disease state (APACHE II: 8 -30)
  - Shows decreased daily living function (ECOG PS: 3 or 4)
- (2) Elective surgery: meets all following criteria;
  - a) Requiring general anesthesia

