## 8.9.2 Assessment Period (from First Dose of Study Medication until Last Assessment Visit)

The qualified rater will assess the efficacy once daily in the morning at least from the day after the first dose of study medication. The participant will complete RCSQ once daily in the morning.

At the last visit, the procedures specified in SoA will be performed in addition to the above.

The clinical coordinator should make sure that the participant has the participant identification card when he/she is discharged.

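### Does scoring missing DRS-R-98 items at the midpoint, with no stated limit, call for a cap or a named robustness analysis?

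*Combined protocol and SAP*

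**What the plan says.** Section 9.6.1 (Secondary endpoints) states the item rule: "Missing responses for the individual items of DRS-R-98 will be scored as the midpoint of the smallest and the largest possible scores". It gives 1.5 as the value for an item rated 0 to 3 and says that the approach matches the one used in the scale's validation. A day's score is set to missing in one case only: "If the assessment is entirely missing on a particular day, the score will be considered missing on that day". Both DRS-R-98 rows of Table 5 repeat these two rules.

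Section 9.4.1 builds both secondary endpoints on the largest daily total in the assessment period. Severity is that maximum. The binary endpoint is "defined as the proportion of participants with the maximum total score of 14.5 or greater during the assessment period".

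For the primary endpoint, Section 9.6.1 counts missing DSM-5 assessments as no delirium and adds a check: "A supportive analysis using survival analytic methods will be conducted to assess the robustness of the conclusion from the primary analysis". No such check is named for the DRS-R-98 item rule, but the opening of the section says: "Methods for supportive analyses and those related to exploratory objectives will be described in the sSAP".

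**The concern.** An item-level imputation rule often comes with a limit on how many items may be filled in before the total is treated as missing. Here there is none. Because the endpoint is a maximum set against a threshold, a single partly scored day can decide a participant's outcome. The rule also has an awkward edge: a wholly missed day adds no event, while a day with a few observed items and many imputed ones can add one.

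Partly scored days are conceivable. Section 8.9.2 says: "The qualified rater will assess the efficacy once daily in the morning at least from the day after the first dose of study medication". In the elective stratum, Section 5.1 admits surgery "Requiring general anesthesia", and Section 4.1 fixes its timing: "The participants hospitalized due to elective surgery will receive surgery on the next day or 2 days after admission/the first dose of study medication". Some ratings therefore fall on the morning after an anaesthetic, and Section 3 lists five DRS-R-98 items on cognitive function that a drowsy participant might not complete.

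At stake would be the reading of the two secondary endpoints. The report might not show how many DRS-R-98 cases rest on observed symptoms and how many only on imputed points. The primary endpoint is not involved.

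**Working it through.** **Inputs from the documents.** Threshold 14.5 on the maximum daily total (Section 9.4.1); 1.5 points per missing item rated 0 to 3 (Section 9.6.1); five cognitive items (Section 3); 5 to 7 doses with rating from the morning after the first dose to the day after the last (Sections 1.3, 8.1.12.1 and 8.9.2); 100 per arm, 30% against 11.6% (Section 9.9.1); a ceiling of about 60% on either hospitalization stratum (Section 6.3.2).

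**Assumptions.** Items are scored 0 to 3 in whole points, as in the plan's example. The number of items, any other item ranges and the frequency of missing items are not in the documents.

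**The plan's own power figure.** Normal approximation, pooled variance under the null, two-sided 0.05:

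- mean proportion = (0.30 + 0.116)/2 = 0.208
- null SE = √(2 × 0.208 × 0.792/100) = 0.0574
- alternative SE = √((0.30 × 0.70 + 0.116 × 0.884)/100) = 0.0559
- z = (0.184 − 1.96 × 0.0574)/0.0559 = 1.28, power 89.95%

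This reproduces the stated 90%. At 13.7% the same method gives 80.1%. These figures belong to the DSM-5 endpoint; the plan states no power for DRS-R-98.

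**Observed points needed.** With k items missing, the smallest qualifying observed sum is 14.5 − 1.5k, rounded up.

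| Items missing | Points imputed | Observed points needed |
|---|---|---|
| 0 | 0 | 15 |
| 1 | 1.5 | 13 |
| 3 | 4.5 | 10 |
| 5 | 7.5 | 7 |
| 9 | 13.5 | 1 |
| 10 | 15.0 | 0 |

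**Like with like.** Setting 7 against 15 compares a shortened scale with a full one. Pro-rated to N equal items, 7 points on N − 5 items correspond to 7N/(N − 5): 14.0 if N = 10, 11.4 if N = 13, 10.2 if N = 16 (illustrative N). The participant is nearer the threshold than the raw 7 suggests, though still below it.

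**Direction.** Suppose five items are missing and 7.5 points are imputed. If each would have scored 0, the total is 7.5 too high. If each would have scored 2, it is 10 − 7.5 = 2.5 too low; if 3, it is 15 − 7.5 = 7.5 too low. Counting missing items as zero would make those last two errors 10 and 15.

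**Exposure.** Completers have 5 to 7 post-dose daily ratings. Participants who stop early, including all who meet DSM-5 delirium, have fewer, because Section 7.1 ends assessment-period procedures at discontinuation. The elective stratum holds about 200 × 0.40 = 80 to 200 × 0.60 = 120 participants. That counts surgical participants, not missing items.

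**Illustrative consequence.** Borrow the primary endpoint's rates and let a fraction f of non-cases in both arms cross 14.5 through imputation alone. The expected number is f × (70 + 88.4).

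| f | Such participants in 200 | Placebo, suvorexant | Difference, points | Power |
|---|---|---|---|---|
| 0 | 0 | 30.0%, 11.6% | 18.4 | 90% |
| 2% | 3.2 | 31.4%, 13.4% | 18.0 | 87% |
| 5% | 7.9 | 33.5%, 16.0% | 17.5 | 82% |
| 10% | 15.8 | 37.0%, 20.4% | 16.6 | 74% |

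Nothing in the documents supports any particular f, and the table leaves out errors in the other direction.

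**The case for a change.** The strongest case for acting is that the text does lack a cap, the arithmetic is right, and no named analysis covers imputed items. The survival analysis for the primary endpoint deals with missing assessments, so it would not help even if it were extended to the DRS-R-98 proportion. The per-protocol analysis in Section 9.5.1 is for the primary endpoint only. Section 4.2.1.1 itself warns that scores alone may not settle whether delirium is present. A table of imputed items would be cheap, because the cognitive and sleep item scores are already needed for exploratory endpoints. Missingness need not be balanced either: Section 2.3 lists somnolence among the main adverse reactions.

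All of that stands as description. It does not show that the rule gives a wrong result. The midpoint value is not in dispute, and read plainly the rule already has a definite answer: impute unless the whole assessment is missing. Nothing in the documents points to a particular cap. Adopting one would alter the main analysis of both secondary endpoints and would need a further rule for how an over-limit day enters the maximum score.

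Scoring missing items as zero gives only a lower bound. The Introduction describes hypoactive delirium as including somnolence and listlessness, so failure to complete an item may itself be a symptom. Many missing items are also less likely than the surgical setting suggests. Section 8.2.2 lets the rater use the medical and nursing record, staff and family; Section 4.2.1.1 has the rating cover the whole interval since the last one; and Section 8.2 requires trained, qualified raters.

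**Conclusion.** No change to the plan is needed. This is a gap in reporting detail that analysts can fill sensibly, not a faulty rule. The effect is confined to two secondary endpoints that carry no formal hypothesis. Each participant classified only through imputed points is worth 1.0 percentage point in one arm of 100. On the borrowed rates, about 8 such participants in 200 would reduce an 18.4-point difference to 17.5. Whether there would be 8, or none, cannot be judged from the documents, and errors can also run the other way.

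The absence of a robustness analysis cannot be established either, since supportive methods are assigned to the sSAP, which is not among the documents. If the sSAP is silent, counting by arm the imputed items and the participants who reach 14.5 only with them would be ordinary good practice and would leave the planned analysis as it is.

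This conclusion rests on whole-point 0 to 3 items and on infrequent item-level missingness. The first follows the plan's example; the second is plausible from the rating procedure but is not documented.
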